## **7. STATISTICAL PLAN**

## 7.1 Sample Size Determination

The choice of sample size is based upon a comparison for the primary outcome (secondary procedures) of THA versus HA. All statistical hypotheses will be two-sided. Alpha levels of 0.05 for the primary and 0.01 for the secondary outcomes were chosen. Previous studies have reported secondary procedure rates in hip fracture patients treated with HA that have ranged from 4 to 10% at one year, with a weighted pooled risk of 5.3% (95% CI 3.2 to 8.9%) in a fixed effect meta-analysis, or 4.9% (95% CI 2.6 to 9.2%) using random effects. A pooled estimate from 5 randomized trials comparing THA with HA gave a relative risk of 1.67 (95% CI 0.86 to 3.24,  $p=0.13$ ) (**Table 3a**).

The sample size calculation reflects the proposed approach to the primary analysis, which will use the Cox proportional hazards model. The calculation is based on methods described by Collett (Collett, 1994). The goal is to calculate the required number of patients that will yield a sufficient number of outcome events (secondary procedures) in order to have adequate statistical power for a given size of treatment effect. This was done taking into account the anticipated secondary procedure rates in the HA group, postulated values of the relative risk increase associated with THA vs. HA, and the rates of mortality and loss to follow-up. Because some of these inputs are expected to change over the two year period of follow-up, the expected number of person-years of follow-up and the expected numbers of study events in each group were calculated, initially for the first year of follow-up; the calculation was then repeated for the second year of follow-up, after having estimated the number of patients in each group who would survive, be event-free, and available for continued follow-up between 12 and 24 months post-randomization.

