Cox proportional hazards modeling was used to estimate the relative effect of THA versus HA on time to mortality, serious adverse events, and hip-related complications, separately, and included the same independent variables as listed for the primary analysis as well as including surgeon as a random effect. The hip-related complications analysis was a competing risk analysis with death as the competing risk. The estimates from the competing risk analysis for clustered data analyses were marginal estimates. We report the HRs and 99% CIs for the proportional hazards models. We performed proportional hazards regressions only for hip-related complications in which there were at least 50 events. Using multi-level models, the effect of THA versus HA on quality of life (SF-12, EQ-5D), function (WOMAC), and mobility (TUG) were estimated separately. Randomized treatment, visit (entered as a categorical variable) were also included as independent variables. Because we believed that the effect of THA versus HA may change over time, we also included an interaction term between treatment and visit. When the interaction term between treatment and visit was not statistically significant at $\alpha=0.05$, we removed it from the model. When the interaction term was significant, we reported the treatment effect at each visit. We accounted for death via joint modelling, using the method described by Rizopoulos.⁷ The SF-12, WOMAC, and EQ-5D were summarized using mean difference (MD) and 99% CIs. We analyzed the TUG as a dichotomous outcome with the following categories: a) patients who complete the test in ≤ 12 seconds, and b) those who require >12 seconds to complete the test or were unable to complete the test. We selected 12 seconds as the cut-off because this was the threshold used by the Centers for Disease Control and Prevention.⁸ The TUG was summarized using odds ratios and 99% CIs. For our multi-level analyses of quality of life, function, and mobility, all available data were used with no imputation performed. The models do not require that a patient have valid scores at all follow-up visits. We chose alpha levels of 0.05 and 0.01 for the primary and secondary outcomes, respectively. When scoring the WOMAC domains, we used the mean of the items that were answered in our calculation if at least 4 of the 5 pain items were answered, at least 1 of the 2 stiffness items were answered, and if at least 14 of the 17 function items were answered. If there were less items answered, the domain was set to missing. To calculate the WOMAC total score, we required non-missing scores for all 3 domains.

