2.11 Interpretation of Blinded Data

Hypothesis: We hypothesize that THA will have similar or lower rates of secondary procedures and higher functional outcome scores at 24 months compared with HA.

Here, we present alternative interpretations of blinded preliminary results. Blinded data interpretation may decrease the frequency of misleading data interpretation. Widespread adoption of blinded data interpretation with a minimum set of recommendations should be widely adopted.¹⁰

Secondary procedures over two years did not differ between treatment groups X and Y. The Kaplan Meier curve for the primary outcome suggests that the hazard ratios (HRs) remain constant up to 1 year (HR=1.30, 95% CI 0.86-1.95, $p=0.217$; non-significant estimates favoring treatment Y) and suggested estimates favouring treatment X after 1 year (up to 2 years) (HR=0.24, 95% CI 0.08-0.73; $p=0.011$).

Deaths did not differ between treatment groups X and Y over a 2-year period ($p=0.493$).

Serious adverse events ($p=0.052$) and hip-related complications ($p=0.277$) between treatment groups X and Y did not differ over a 2-year period.

Treatment X demonstrated significantly better overall WOMAC and EQ-5D utility scores ($p<0.05$) compared to Treatment Y (and trended towards better SF-12 PCS scores) over a 2-year period. TUG scores (cut-off 12 seconds) did not differ between treatment groups ($p=0.181$).

Subgroup analyses did not show any differences in the treatment effect between different subgroups ($p>0.05$).

Given the above preliminary findings, the more plausible hypothesis follows. Treatment X is THA and Treatment Y is HA. THA does not result in a statistically significant difference in secondary procedure rates over a 2-year period compared to HA; however, our findings suggest THA may have more secondary procedures earlier (less than 1 year, possibly driven by higher dislocations *results still blinded*) and HA may have more secondary procedures after 1-year post-fracture in those who did not have a secondary procedure during the first year. Functional outcome scores over 2 years favour THA compared to HA. These differences in function are small (although statistically significant). A lack of difference in secondary procedures, hip-related complications, and deaths, a lack of subgroup effects, and modest improvements in function render THA mildly superior to HA over 2 years. It's not unreasonable to consider the two treatments similar given

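### SAP 2.11 calls WOMAC and EQ-5D significant on p<0.05 although secondary outcomes were assigned 0.01, and it reads serious adverse events at p=0.052 as no difference and omits them from both conclusions

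*SAP*

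**What the plan says.** **Level and intervals.** Protocol 7.1 states: "Alpha levels of 0.05 for the primary and 0.01 for the secondary outcomes were chosen", and "All statistical hypotheses will be two-sided". SAP 2.8 repeats this: "We chose alpha levels of 0.05 and 0.01 for the primary and secondary outcomes, respectively".

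SAP 2.8 attaches 99% intervals to both kinds of secondary outcome. For time to death, serious adverse events (SAEs) and hip-related complications: "We report the HRs and 99% CIs for the proportional hazards models". For function and quality of life: "The SF-12, WOMAC, and EQ-5D were summarized using mean difference (MD) and 99% CIs". TUG, analysed as an odds ratio, also gets a 99% interval.

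**Results as worded in SAP 2.11.** On function: "Treatment X demonstrated significantly better overall WOMAC and EQ-5D utility scores", supported only by p<0.05. SF-12 PCS is described as trending the same way, with no p-value. SAEs (p=0.052) and hip-related complications (p=0.277) are covered by one statement, that results "between treatment groups X and Y did not differ over a 2-year period". Deaths (p=0.493) and TUG (p=0.181) are also said not to differ.

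**Conclusion.** Two mirror-image versions are given, one for each possible identity of X. Each starts its summing-up with "A lack of difference in secondary procedures, hip-related complications, and deaths", adds the absence of subgroup effects and a modest functional gain, and concludes that one treatment is mildly superior. SAEs appear in neither list, although SAP 2.6 defines them as a secondary outcome and SAP 2.8 gives them their own model.

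**The concern.** Section 2.11 records how the results would be read before the arms were identified, and its stated purpose is to make misleading interpretation less likely. Three features work against that.

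1. Function is the only item in the summing-up that separates the treatments, and its significance is asserted at a level that the plan does not use for secondary outcomes. If WOMAC and EQ-5D do not reach 0.01, the grounds for superiority fail by the plan's own rule.
2. A non-significant SAE result is reported as no difference, without the estimate a reader would need to judge it.
3. The harm outcome with the smallest p-value (0.052, against 0.277 and 0.493) is the one left out of the benefit-harm statement, while a functional score with no stated p-value is credited with a trend.

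At stake is whether the overall statement follows from the analysis that was planned, and whether it reflects all the safety outcomes.

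**Working it through.** **Inputs**
- Level 0.05 for the primary and 0.01 for secondary outcomes, two-sided (Protocol 7.1; levels repeated in SAP 2.8).
- 99% intervals for harms and for SF-12, WOMAC, EQ-5D and TUG (SAP 2.8).
- SAEs p=0.052, with no hazard ratio (HR), interval or direction (SAP 2.11).
- WOMAC and EQ-5D p<0.05, with no exact value, mean difference or interval (SAP 2.11).
- Primary outcome, X against Y: HR 1.30 (95% CI 0.86-1.95), p=0.217 up to 1 year; HR 0.24 (0.08-0.73), p=0.011 after 1 year (SAP 2.11).

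**Step 1: reproduce the figures that can be checked.** SE = (ln U - ln L)/(2 x 1.960); z = ln(HR)/SE.
- Up to 1 year: SE = 0.209, z = 1.256, p = 0.209. Rounding of the inputs allows 0.198 to 0.220; the stated value is 0.217.
- After 1 year: SE = 0.564, z = -2.530, p = 0.0114. Rounding allows 0.008 to 0.016; the stated value is 0.011.

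Both agree, so a normal (Wald) approximation is adequate for what follows.

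**Step 2: SAEs against each level.** A two-sided p of 0.052 gives |z| = 1.943. The critical values are 1.960 at 0.05 and 2.576 at 0.01. SAEs are non-significant at both, so this verdict does not depend on the level.

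**Step 3: what p=0.052 implies for the interval.** On the log scale the half-width relative to the estimate is 1.960/1.943 = 1.009 at 95% and 2.576/1.943 = 1.326 at 99%. Whatever the HR, the 95% interval passes the null by only about 1% of the log-HR, and the 99% interval by about 33%.

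The HR is not given, so the values below are assumptions. They are shown in both directions because the documents do not say which arm had more SAEs. The second row of each pair is the reciprocal of the first.

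| Assumed HR | 95% CI | 99% CI |
|---|---|---|
| 1.10 | 0.999-1.21 | 0.97-1.25 |
| 1/1.10 = 0.91 | 0.83-1.001 | 0.80-1.03 |
| 1.20 | 0.998-1.44 | 0.94-1.53 |
| 1/1.20 = 0.83 | 0.69-1.002 | 0.65-1.06 |
| 1.30 | 0.998-1.69 | 0.92-1.84 |
| 1/1.30 = 0.77 | 0.59-1.002 | 0.54-1.09 |

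In every row the data are compatible with a sizeable difference and barely compatible with none.

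**Step 4: WOMAC and EQ-5D against the declared level.** p<0.05 says only that |z| exceeds 1.960, whereas 0.01 needs |z| above 2.576. Any p between 0.01 and 0.05 gives a 99% interval that includes zero. Whether the two scores pass cannot be settled from what is reported.

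**Step 5: the cost of 0.01, and who bears it.** An effect with 80% power at 0.05 has z centred at 1.960 + 0.842 = 2.802. At 0.01 its power is Phi(2.802 - 2.576) = Phi(0.226), about 59%. This loss applies equally to harms and to functional outcomes.

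**The case against.** A reader might infer that harms face a stricter test than benefits. The documents contradict this as a statement about the plan: both get 0.01 and 99% intervals. Nor does 2.11 say which level was applied to SAEs, and at 0.05 they would still be non-significant.

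A reader might also infer that the conclusion is tilted towards one arm, or that an SAE excess of some size has been hidden. No direction is reported. If SAEs were more frequent under Y, leaving them out understates the case for X. The upper limits in the table come from assumed hazard ratios and are not results.

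It would also go too far to say that WOMAC and EQ-5D fell short of 0.01, since p<0.05 may stand for values well below it.

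Further points in the plan's favour:
- The no-difference wording is not reserved for harms; the primary outcome and TUG get it too.
- The section calls its results preliminary, describes the functional differences as small, and allows that the treatments may be considered similar.
- SAE hazard ratios with 99% intervals are already specified in SAP 2.8.

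All of this stands, and it limits the point to how 2.11 applies and words the results. It does not answer three things: significance is claimed on a threshold other than the declared one, non-significance is reported as no difference without an estimate, and a defined secondary safety outcome is absent from both summaries.

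**Conclusion.** The point holds as an inconsistency between SAP 2.8 and SAP 2.11 that can change the stated conclusion. It does not alter any planned analysis.

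- **Function.** Significance at the declared 0.01 is not demonstrated. If either score lies between 0.01 and 0.05, calling it statistically significant is wrong under the plan. If neither meets 0.01, the mild superiority claimed in both versions loses its basis.
- **SAEs.** p=0.052 (|z|=1.943) is non-significant at both levels but does not show absence of difference; the 95% interval only just includes 1. Omitting SAEs leaves the benefit-harm statement incomplete in both versions. Which arm it would favour is unknown.

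The SAE interval statements assume that the p-value comes from a Wald-type test of the log hazard ratio. The table also rests on the assumed hazard ratios. The mismatch of levels and the omission need no assumption.

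**What to change.** In SAP 2.11:

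1. Give exact p-values, mean differences and 99% intervals for WOMAC and EQ-5D, judge them at 0.01, and remove the claim of statistical significance from both versions for any score that does not meet it.
2. For SAEs, deaths and hip-related complications, replace the no-difference wording with the hazard ratio, its direction in terms of X or Y, and the planned 99% interval. A 95% interval may be added as a supplement. Moving only the harms to 95% would depart from the pre-set level and create an asymmetry of its own.
3. Include SAEs in the summing-up of both versions, and treat near-significant results alike, so that SF-12 PCS and SAEs are each described by estimate and interval.

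SAP 2.9 shows that unblinding has since taken place, so a dated correction is preferable to overwriting the blinded text.

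The cost is wording plus output from models already planned; no new data are needed. The downside is that the overall statement may become less definite.

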2.8 Statistical Analyses for Primary and Secondary Outcomes

Analyses included patients in the groups to which they were assigned. Patients were censored at 24 months of follow-up or at the time of their last follow-up for patients lost to follow-up. The primary analysis was a proportional hazards model using a competing risk analysis (death as the competing risk) with time to the HEALTH primary study endpoint as the outcome. The independent variable was THA versus HA, and the following covariates were used: age (50-80 years or >80 years), pre-fracture living setting (institutionalized or not institutionalized), pre-fracture functional status (using aid or independent ambulator), and ASA Class (Class I/II or III/IV/V). For these covariates, we used values that were entered into the minimization system at time of enrollment. For our competing risk analyses, we used the method described by Zhou et al. to account for clustering within surgeons.⁶ The estimates from the competing risk analysis for clustered data analyses were marginal estimates. We report the treatment effects as hazard ratios (HRs) with 95% confidence intervals (CIs). No adjustment for multiplicity was made and the 95% CIs do not adjust for multiplicity. Kaplan-Meier curves were constructed for the primary outcome.

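### SAP 2.11 calls the WOMAC and EQ-5D differences significant on p<0.05 alone, while the plan sets 0.01 and 99% intervals for these outcomes

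*SAP*

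**What the plan says.** The rule is stated in both documents. Protocol 7.1: "Alpha levels of 0.05 for the primary and 0.01 for the secondary outcomes were chosen". SAP 2.8: "We chose alpha levels of 0.05 and 0.01 for the primary and secondary outcomes, respectively". SAP 2.8 also fixes the reporting of the patient-reported scores: "The SF-12, WOMAC, and EQ-5D were summarized using mean difference (MD) and 99% CIs". Protocol 3.2.2 and SAP 2.6 list WOMAC and EQ-5D among the secondary outcomes.

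SAP 2.11 then describes the blinded results as follows: "Treatment X demonstrated significantly better overall WOMAC and EQ-5D utility scores ($p<0.05$) compared to Treatment Y". Both of its scenarios for what X and Y might be repeat the claim: "These differences in function are small (although statistically significant". Both scenarios also reach their overall judgement with the same list: "A lack of difference in secondary procedures, hip-related complications, and deaths, a lack of subgroup effects, and modest improvements in function render" one arm slightly better over two years.

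Protocol 7.1, after setting 0.01, computes sample sizes for SF-12, WOMAC and EQ-5D at alpha 0.05 and 80% power: 128, 90 and 128 patients in total.

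**The concern.** A p-value below 0.05 may or may not be below 0.01. The wording of 2.11 treats the first as enough, although the plan asks for the second. The same section gives exact p-values for deaths (0.493), serious adverse events (0.052), hip-related complications (0.277) and TUG (0.181). The two secondary outcomes claimed as positive have only an upper bound.

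Function is the one positive item in the list behind the overall judgement; every other item is an absence of difference. For the primary analysis SAP 2.8 says: "No adjustment for multiplicity was made and the 95% CIs do not adjust for multiplicity". The visible text describes no multiplicity procedure for the secondary outcomes, so the 0.01 level is the only stated limit on chance findings among them. If that level is not applied, the limit has no effect on the one conclusion where it is needed.

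The sizing at 0.05 is a separate and smaller inconsistency inside protocol 7.1.

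**Working it through.** **1. Where the two thresholds disagree.** The two-sided normal quantiles are 1.960 (alpha 0.05) and 2.576 (alpha 0.01). Their ratio is 2.576 / 1.960 = 1.31, so a 99% interval is 1.31 times as wide as a 95% interval. An estimate passes 0.05 and fails 0.01 only if it lies between 1.96 and 2.58 standard errors from zero. Section 2.11 gives no estimate, standard error or interval for WOMAC or EQ-5D, so their position cannot be recovered.

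**2. What the 0.01 level controls.** Section 2.11 names seven secondary outcomes: deaths, serious adverse events, hip-related complications, WOMAC, EQ-5D utility, SF-12 physical score and TUG. The chance of at least one false claim, if none truly differs, is:

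| | alpha 0.01 | alpha 0.05 |
|---|---|---|
| Upper bound, 7 × alpha | 7% | 35% |
| If independent, 1 − (1 − alpha)^7 | 6.8% | 30.2% |

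This is a property of the thresholds and not evidence about this trial's results.

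**3. How large the ambiguous band could be (illustration only).** Inputs from protocol 7.1 are SD 15 (WOMAC function, applied here to the total score), SD 0.20 (EQ-5D), annual mortality of 15% and annual loss of 5%. Retained at 24 months: 1,434 × (0.85 × 0.95)² = 935, or 467.5 per arm. The band is z × SD × √(2/467.5), with √(2/467.5) = 0.0654.

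- WOMAC: 1.960 × 15 × 0.0654 = 1.92 and 2.576 × 15 × 0.0654 = 2.53 points, which is 21% to 28% of the protocol's 9-point difference.
- EQ-5D: 1.960 × 0.20 × 0.0654 = 0.026 and 2.576 × 0.20 × 0.0654 = 0.034, which is 26% to 34% of the protocol's 0.10.

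With all 1,434 patients the bands are 1.55 to 2.04 points and 0.021 to 0.027. A difference that 2.11 itself calls small could fall in such a band. The multi-level joint model in SAP 2.8 would give other standard errors.

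**4. The secondary sample sizes.** These use a two-sample t-test, two-sided, 1:1, with 80% power. The standardised differences are 4/8 = 0.5 (SF-12), 9/15 = 0.6 (WOMAC) and 0.10/0.20 = 0.5 (EQ-5D). The plan's own figures are reproduced first, at 0.05:

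| Outcome | Stated per arm | Recomputed, 0.05 | Recomputed, 0.01 | Total, 0.01 | Power at 0.01 with stated size |
|---|---|---|---|---|---|
| SF-12 | 64 | 63.8 → 64 | 95.1 → 96 | 192 | 58.5% |
| WOMAC | 45 | 44.6 → 45 | 66.6 → 67 | 134 | 58.6% |
| EQ-5D | 64 | 63.8 → 64 | 95.1 → 96 | 192 | 58.5% |

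The stated sizes reproduce exactly at 0.05, so that is the level used. At 0.01 the restated sizes give 80.5%, 80.3% and 80.5% power. With 935 patients retained, power at 0.01 exceeds 99.9% for each difference.

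**The case against.** The strongest reply is that no error of analysis is shown. A result reported as p<0.05 may also satisfy 0.01, SAP 2.8 holds the right rule, and 2.11 is a preliminary narrative written while still blinded. It calls the differences small, allows that the treatments may be regarded as alike, and closes in both scenarios with doubt about THA as first choice. All of this stands and limits the stakes. It does not remove the mismatch: 2.11 attaches the word significant to a level other than the one the plan set.

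Other objections stand in part:

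- The SAP text before section 2.0 was not available for this review and may hold the exact values. If so, a cross-reference is enough.
- Two outcomes carry the functional claim, so a miss on one would weaken the overall judgement and not empty it. Only a miss on both would leave it without support at the pre-set level.
- The multiplicity sentence in SAP 2.8 sits with the primary analysis, and the seven outcomes are those mentioned in 2.11, not a declared family. The 7% and 35% figures show what the threshold does and no more.
- A note added now would postdate unblinding, since SAP 2.9 already reports work done after it. That is why the note should be dated and kept apart from the blinded text.
- The sizing point changes no decision, because 1,434 is ample at either level.

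**Conclusion.** The concern holds as a statement about the visible text. SAP 2.11 labels two secondary outcomes significant on p<0.05, against a level of 0.01 set in both documents, and does not show that 0.01 is met. Whether it is met cannot be determined from 2.11.

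The consequence is moderate. The discrepancy matters only if an estimate lies between 1.96 and 2.58 standard errors, and it would affect the slight-superiority judgement, not the closing statements on implant choice. That 1.96-to-2.58 range rests on normal quantiles alone. The bands in score points rest on the protocol's SDs, its attrition rates and a single-visit comparison, and are illustrative.

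The inconsistency in protocol 7.1 is certain but minor: the secondary sizes are right at 0.05 and too small at the 0.01 set earlier in the same section. The trial size is unaffected.

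**What to change.** Leave the blinded interpretation in SAP 2.11 as written. Add a dated note giving, for WOMAC and EQ-5D, the exact p-value, mean difference and 99% confidence interval from the SAP 2.8 model, judged against 0.01. The form follows the rule in SAP 2.8: "When the interaction term was significant, we reported the treatment effect at each visit". If the treatment-by-visit term was removed, one overall difference is enough. If either outcome misses 0.01, the note should say that the significance wording and the slight-superiority conclusion do not meet the pre-set level for that outcome. If the values already stand elsewhere in the SAP, a cross-reference suffices.

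In protocol 7.1, restate the secondary sizes at two-sided alpha 0.01 and 80% power as at least 192 (SF-12), 134 (WOMAC) and 192 (EQ-5D) in total, and state that 1,434 remains ample.

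The cost is two p-values and two intervals (by visit if the interaction was kept) from an analysis already specified, plus three restated figures. No patients, new analyses or changes to the blinded record are needed. The downside is that the functional claim may weaken.

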Based upon aggregate data from the pilot study, annual mortality rates of 15% and a loss to follow-up of 5% in each group were assumed, these rates applying to each of the two years of follow-up. Informed by the meta-analysis, the following assumptions were made: a one year risk of having a secondary procedure of 5% in the HA group and a risk of 1% in the second year. Various values of the relative risk reduction (HA vs. THA) were then used to identify the specific value that would correspond to a cumulative risk difference between THA and HA of 5% after 2 years. This figure was identified in a survey of participating surgeons as the minimally important difference to clinicians. Annual event risks by group were converted into equivalent hazard rates, assuming for simplicity that the hazard rate would be approximately constant within each of the two years. It is estimated that approximately 72% of the group receiving THA and 76% of the group receiving HA will be event-free and available for further follow-up at the start of the second year. The sample size was increased to allow for a combined 7.6% crossover rate from the assigned to the alternate treatment, based on pilot data. These assumptions lead to a required total sample size of 1,316 patients, which will yield an expected number of 96 secondary procedures. The associated relative risk reduction (RRR) is 0.45.

These calculations were repeated after replacing the 5% event risk at one year for HA by 4% and 6% and leaving the other factors unchanged (**Table 3b**). To account for potential surgeon level effects, the sample size has been further increased by 9% to 1,434.

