For the secondary outcomes, an important difference in SF-12 is considered to correspond to a moderate effect as reported by Cohen (Cohen, 1988) as well as a minimally important difference in the SF-12 as reported by Ware (Ware & Sherbourne, 1992). In both cases, the value is at least half the standard deviation, equivalent to 4-point difference in score. Specifying an alpha level=0.05, a beta=0.20 (study power=80) and a standard deviation of 8 (Jaglal et al, 2000), a sample of at least 128 patients (64 per group) is required to ensure detection of a half standard deviation improvement. In clinical drug trials, a 9-point change in WOMAC functional score was accepted as a minimally significant improvement in symptoms (Turbach et al, 2005). In this study, at least 90 patients (45 per group) would be required to detect this difference (alpha level=0.05, beta=0.20,  $\sigma = 15$ ). Previous studies have found a standard deviation of 0.20 for the EQ-5D (Tidermark et al, 2003). To detect a difference of 0.10 (half the standard deviation) with 80% power at an alpha level of 0.05, this study requires a total of 128 patients (64 per group). Thus, in all circumstances, the desired sample size of **1,434 patients** will be sufficient to detect clinically meaningful differences in the secondary measures of outcome.

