2.9 Subgroup Analyses and Hypothesized Effects

At the trial onset, we specified in the trial protocol that no subgroup analyses would be conducted. However, towards the end of the trial, prior to unblinding, the following subgroup analyses were decided upon and were conducted to investigate the following prognostic factors as possible effect modifiers. The HEALTH primary endpoint was the dependent variable for these analyses. For these subgroup analyses, we used the data from our database. What was captured in the database reflects the true values for these factors, which may be different than what was originally entered into the minimization system at time of enrollment.

1. Age (i.e., 50-80 years or >80 years): Hypothesized that THA will be better relative to HA in the younger subgroup than in the older patients.
2. Pre-fracture living setting (i.e., institutionalized or not institutionalized): Hypothesized that THA will be better relative to HA in those not institutionalized than those institutionalized.
3. Pre-fracture functional status (i.e., using aid or independent ambulator): Hypothesized that THA will be better relative to HA in independent ambulators than in those using an aid.
4. American Society for Anesthesiologists (ASA) Class (i.e., Class I/II or III/IV/V): Hypothesized that THA will be better relative to HA in Class I/II than in Class III/IV/V.

These subgroup analyses were performed (separately) by including the subgroup factor as an independent variable in our proportional hazards regression model along with an interaction term between it and randomized treatment. We used the criteria suggested by Kasenda et al. to guide inferences about the credibility of our subgroup analyses.⁹

After unblinding, we identified three post hoc subgroup analyses and performed them as follows:

1. Added a three-category age (50 to 70 years or 71 to 80 year or ≥ 81 years) as an independent variable in our proportional hazards regression model along with an interaction term between it and randomized treatment. We hypothesized that THA will be better relative to HA in the youngest subgroup than in the older patient subgroups.
2. Added a three-category age (50 to 70 years or 71 to 80 year or ≥ 81 years) as an independent variable and interaction of age with treatment group into our final WOMAC total score model. We hypothesized that THA will be better relative to HA in the youngest subgroup than in the older patient subgroups.

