3. Added country (Canada or Netherlands or USA or Australia or Norway or Spain or UK or Finland or New Zealand or South Africa) as an independent variable in our proportional hazards regression model along with an interaction term between it and randomized treatment. We hypothesized no difference across countries in treatment effects.

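### SAP 2.11 treats non-significant subgroup tests on about 105 events as absence of subgroup effects and uses that as a ground for a verdict that rests on function

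*SAP*

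**What the plan says.** SAP section 2.11 (Interpretation of Blinded Data) sets out two readings of the masked results, one for each possible identity of treatments X and Y. The subgroup finding is one sentence: "Subgroup analyses did not show any differences in the treatment effect between different subgroups", followed only by p>0.05. No interaction estimate or interval is given. The reading in which X is THA then concludes that "a lack of subgroup effects, and modest improvements in function render THA mildly superior to HA over 2 years". The reading in which X is HA uses the same grounds for HA.

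SAP section 2.9 names four factors chosen late in the trial but before unblinding: age, living setting, walking status and ASA class. On the outcome it says: "The HEALTH primary endpoint was the dependent variable for these analyses". It gives each factor a directional hypothesis, with THA relatively better in the younger, non-institutionalised, independently walking or ASA I/II patients. Three further analyses were added after unblinding. One of them, three-category age on the WOMAC total score, is the only subgroup analysis of function.

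Protocol section 7.2.3 planned no subgroup analyses. Protocol section 7.1 sizes the trial for the main effect only: "a required total sample size of 1,316 patients, which will yield an expected number of 96 secondary procedures", later raised by 9% to 1,434 patients.

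**The concern.** There are two gaps between the evidence and its use.

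- **Precision.** A p-value above 0.05 for an interaction shows that none was detected. It becomes evidence of a common effect only if the interval is narrow enough to rule out differences that matter. Section 2.11 shows no interval, and the trial was sized for the main effect. Because the SAP itself predicted heterogeneity for all four factors, a weak null test says little against those predictions.
- **Endpoint.** What makes one arm slightly better in section 2.11 is function. The four factors were tested on secondary procedures. A null interaction on procedures does not show that the functional gain is the same in, say, institutionalised patients or those over 80.

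If the wording passes into the final conclusions, consistency across patient types would be offered as a finding that the analyses cannot deliver for procedures and did not examine for function.

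**Working it through.** **Inputs**

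- Primary alpha 0.05, two-sided (protocol 7.1: "All statistical hypotheses will be two-sided. Alpha levels of 0.05 for the primary and 0.01 for the secondary outcomes were chosen").
- Power 80%. The protocol states this only for the secondary outcomes ("Specifying an alpha level=0.05, a beta=0.20 (study power=80) and a standard deviation of 8"); it is assumed here for the primary.
- Effect size: "The associated relative risk reduction (RRR) is 0.45", so HR 0.55. Crossover allowance 7.6% (protocol 7.1).
- Blinded HRs (SAP 2.11): 1.30 (95% CI 0.86 to 1.95) in year 1 and 0.24 (0.08 to 0.73) in year 2.
- Subgroup shares of events: not in the documents, so assumed from 50/50 to 90/10.

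**Step 1: reproduce the plan's 96 events.** Schoenfeld: 4 × (1.96 + 0.84)² / (ln 0.55)² = 4 × 7.85 / 0.357 = 87.8, so 88. With crossover, 88 / (1 − 0.076) = 95.2, so 96. The figure reproduces.

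**Step 2: events available at 1,434 patients.**

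- Scaling the plan: 96 × 1,434 / 1,316 = 104.6.
- From the blinded intervals, SE = (ln upper − ln lower) / 3.92, which gives 0.209 and 0.564. Events ≈ 4/SE² = 91.7 + 12.6 = 104.
- Allowing for unequal events by arm, (1 + HR)² / (HR × SE²) = 93.3 + 20.1 = 113.

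The working value is 105, with a range of 96 to 113.

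**Step 3: precision of a two-level interaction.** With D events, share q in one subgroup and 1:1 allocation, SE of the log ratio of HRs = √[4/(Dq) + 4/(D(1 − q))]. The 95% CI factor is exp(1.96 × SE). The ratio detectable with 80% power is exp(2.80 × SE). Power for a true ratio r is Φ(ln r / SE − 1.96). For D = 105:

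| Split | SE | 95% CI factor | Detectable at 80% power | Power, twofold | Power, threefold |
|---|---|---|---|---|---|
| 50/50 | 0.390 | 2.15 | 2.99 | 43% | 80% |
| 75/25 | 0.451 | 2.42 | 3.54 | 34% | 68% |
| 80/20 | 0.488 | 2.60 | 3.92 | 29% | 61% |
| 85/15 | 0.547 | 2.92 | 4.62 | 24% | 52% |
| 90/10 | 0.651 | 3.58 | 6.19 | 19% | 39% |

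**Step 4: what non-significance leaves open.** In the best case (even split, estimate exactly 1) the interval is 0.47 to 2.15. More generally, at an even split any 95% interval spans a ratio of 2.15² = 4.6 from end to end. If it contains 1, it must reach at least 2.15-fold in one direction. An estimate just short of p = 0.05 would have an upper limit of about 4.6 (50/50) or 6.8 (80/20).

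**Step 5: sensitivity to the event count.** At an even split, 96 events give a factor of 2.23 and 113 give 2.09; power for a twofold ratio is 40% and 45%. Bringing the factor down to 2 would need 16 × (1.96 / ln 2)² = 128 events.

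**Step 6: what function could show.** Patients left at 24 months under the protocol's yearly 15% mortality and 5% loss: 1,434 × 0.85² × 0.95² = 935. With the protocol's SD of 15 for WOMAC function, SE = 15 × √[4/(935q) + 4/(935(1 − q))]. The interaction detectable with 80% power is:

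| Split | Alpha 0.05 | Alpha 0.01 (secondary outcomes) |
|---|---|---|
| 50/50 | 5.5 points | 6.7 points |
| 90/10 | 9.2 points | 11.2 points |
| 95/5 | 12.6 points | 15.4 points |

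The protocol's minimally significant change is 9 points. This uses one visit; the repeated-measures model would add some precision.

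**The case against.** Section 2.11 is a deliberate record of how masked results were read, written for both possible identities. Its value lies in staying as written, so editing it after unblinding would be wrong. That stands, and it moves the correction to the final report.

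The subgroup statement is one ground among several. Section 2.11 also says the two treatments could reasonably be considered similar and that THA may not be the implant of choice. A reader might infer that the plan tells surgeons the effect is uniform across patients. The text does not go that far, and the verdict could be argued without this ground.

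Restricting the four factors to the primary endpoint, with stated directions and cited credibility criteria, is a defensible choice. New interactions on function would be chosen after unblinding, and Step 6 shows they would be imprecise for lopsided factors. That also stands, so such models cannot be presented as the remedy.

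A reader might also cite the country interaction against section 2.11. SAP 2.9 places it after unblinding, so it cannot underlie the blinded statement, and the documents give no enrolment by country from which to judge it.

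None of this supports reading p>0.05 as absence of effect modification.

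**Conclusion.** The point holds. The inference from non-significant interactions to no subgroup effects is unsupported, and it is used for a conclusion about an outcome on which the four factors were not tested.

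A twofold difference between subgroup HRs cannot be excluded in both directions by any of these tests, even with an even split and a null estimate. Power to detect one is 43% at best with 105 events, and 45% with 113.

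A reader might go further and infer that threefold differences are also left open. The documents do not establish that. The detectable ratio of about 3 is a statement about power; what is excluded depends on the confidence interval. With 105 events, a near-null estimate would exclude threefold for splits up to about 85/15, but not at 90/10 or when the estimate lies well away from 1.

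The result rests on a derived event count, assumed subgroup shares, and an SE formula that ignores surgeon clustering and the competing risk of death, although the counts back-calculated from the reported intervals absorb some of that.

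**What to change.** 1. Keep section 2.11 unchanged as a dated record of the blinded interpretation.
2. In the final conclusions, replace the claim that subgroup effects are absent with: *no subgroup effect on secondary procedures was detected; power to detect one was low.*
3. Report each of the four interactions as a ratio of HRs with its 95% CI and the events per subgroup and arm. Let the intervals show what is excluded; do not write that sentence in advance.
4. Do not cite the subgroup result in support of the verdict on function.
5. Optional: fit the four interactions to WOMAC and EQ-5D, labelled post hoc and exploratory, with a note that precision is limited for unbalanced factors.

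The cost is a few sentences and one table from models already fitted. Item 5 would add model runs on existing data. No new data are needed, and the conclusion becomes slightly less tidy.
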